Our Primary Outcome is change in the modified Harris Hip Score at 12 months and 24 months. Secondary outcomes include changes in other validated outcomes measures patient satisfaction, and degree of improvement on physical exam. The influence of OA severity (Outerbridge scoring) and location of OA will also be analyzed to determine if they have an effect on the aforementioned outcome measures. Satisfaction will be assessed by an exit questionnaire (See section IV). In addition to gauging satisfaction, this questionnaire will ask subjects how they felt about their participation in the study. (See section IV)

Inclusion and Exclusion Criteria:

Inclusion criteria	Rationale
Age 40 or greater	Higher likelihood of undetectable OA on imaging
Orthopedic surgeon determines symptoms are consistent with a labral tear.	Required for treatment
Availability of hip radiographs and MRI	Needed to assess eligibility and comparison for specific aim 3
Willingness to undergo randomization and ability to understand and sign informed consent document	Ability to understand study and consent willingly

Exclusion criteria	Rationale
Unexpected pathology at the time of arthroscopy	Source of pain less likely to due dysfunction of the labrum and more likely due to aberrant extra-articular biology
Same site surgery	Complex anatomy
Contraindication to surgery or physical therapy	Cannot tolerate either treatment grouping
Alternate form of PT for greater than 6 weeks	Will negatively augment results. May affect recruitment.

Selection and enrollment:

We will enroll 122 consecutive subjects meeting the aforementioned criteria. Subjects will be randomized into conservative or surgical treatment arms. All potential subjects on the clinic schedule of the investigator will be pre-screened for eligibility based on age, clinical assessment, and previous medical history.

All eligible subjects will be approached at an outpatient clinic visit. Those who initially meet inclusion criteria will be introduced to the study and given a research consent form that they have the opportunity to take home and to review.

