The mean outcome scores of the mHHS in each treatment group at 12 months will be compared to baseline scores to assess for significant differences using paired sample t-test in SPSS 16 (SPSS, Chicago, IL). The mean outcomes scores of the mHHS between groups at 12 months will be compared using independent t-tests to assess for significant difference. We will use a Levene test to judge variance and proceed accordingly. If a statistically significant difference is detected during these analyses, we will calculate the effect size (ES) to determine how meaningful these results are outside of being statistically significant. The ES will be calculated by: [(mean mHHS score of surgical arm / mean mHHS of the conservative group) / standard deviation of the conservative group]. According to Cohen ⁵⁸, an ES <0.1 is trivial, ES of 0.1-0.3 is minimal, ES of 0.3-0.5, is moderate, and ES >0.5 is large. We will repeat the same analysis at 12 months.

Hypothesis 2.1, 2.2, and 2.3:

Diagnosis and treatment of the prearthritic and early arthritic hip has been an area of intense interest. However, our most conventional method of assessment (plain radiography) does not provide us with enough diagnostic sensitivity.⁴¹ Direct visualization on the articular surfaces in the hip is both sensitive and specific. Furthermore, emphasis is being placed on the location of arthritis as a prognostic indicator of good outcomes following hip arthroscopy. The value of arthroscopic techniques for primary

symptoms and/or prevention of OA secondary to labral tears remains unclear even though preliminary reports indicate there may be some benefit to repairing a torn labrum, even in cases of severe OA. Evaluation of arthritic change at the time of arthroscopy is important, particularly in subjects where there remains uncertainty about the efficacy of labral repair for those with articular or rim cartilage degeneration that the effects of those changes on long-term OA progression.⁵⁹

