Using the data from our retrospective review of outcomes following labral repair, a 10 point or greater difference on the mHHS as significant, and a single-tail independent t-test to evaluate the difference between means with 80% power and a 5% significance level, 35 subjects are needed to demonstrate a statistically significant difference between the average mHHS of the conservative group and surgical group. Testing of hypothesis 1.5 will be an intragroup analysis looking for a significant difference in outcome measures from the time of completion of PT (non-crossover) when compared to the same data to be collected at 12 months and 24 months. The purpose is to determine the short-term durability of the response to PT, if one is found.

70 study completers should provide us with the necessary data needed to substantiate or reject our hypothesis. There has been no prospective trial to date testing these hypotheses in the hip, but we expected a 7.3-10.3% dropout rate based on the results of a similar study in the knee. However, as of July 2018, we had 47 patients that had passed the 2-year follow-up mark, of which 5 patients were no longer in the study (combination of lost to follow-up and proceeding to total hip arthroplasty), and another 11 had yet to complete their 2-year surveys even with multiple attempts to contact them and encourage them to do so. With a yield of 31 patients out of 47, or 65.95%, we increased our sample size to 122.

Therefore, we estimate needing 122 subjects to achieve 70 study completers, in the appropriate proportion of 35 subjects per treatment arm. We enroll until reaching at least 35 subjects in each group.

The results of the MeTeOR trial in the knee show that we can expect a higher drop-out rate in the surgical group. As such, this cohort may be our limiting factor.^{40, 43, 61, 62}

Specific Aim 2. Hypotheses 2.1-2.3: *To evaluate the significance of arthritic burden on short term outcomes following arthroscopic labral repair.*

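### The between-arm mHHS t-test has no missing-data method, so its 24-month result can be biased by arm-related dropout that extra enrolment does not correct

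*Combined protocol and SAP*

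**What the plan says.** Section III (Study Overview) defines the endpoint: "Our Primary Outcome is change in the modified Harris Hip Score at 12 months and 24 months". Section V (Hypothesis 1.1-1.4) gives the between-arm test: "The mean outcomes scores of the mHHS between groups at 12 months will be compared using independent t-tests to assess for significant difference". It then says "We will repeat the same analysis at 12 months". Since Hypothesis 1.4 and the endpoint both extend to 24 months, I read that sentence as meant for 24 months; this is an inference.

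The Power Analysis for Specific Aim 1 sets its target difference at 10 mHHS points. Its sizing rule reads: "a single-tail independent t-test to evaluate the difference between means with 80% power and a 5% significance level, 35 subjects are needed". It states that "70 study completers should provide us with the necessary data needed to substantiate or reject our hypothesis". Of 47 subjects past two years in July 2018, 5 had left (lost to follow-up or hip arthroplasty) and 11 had not returned the 2-year surveys. The response given there is: "With a yield of 31 patients out of 47, or 65.95%, we increased our sample size to 122". Citing the knee trial, the section adds that "we can expect a higher drop-out rate in the surgical group".

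Section III (Study retention procedures) provides for remote completion, e-mailed surveys and reminder calls. Missing data are otherwise mentioned only in Section IV, as something the data-capture software reports. No analysis set, imputation, repeated-measures model or missing-data sensitivity analysis is stated.

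**The concern.** A t-test at one time point, with no rule for absent scores, drops every subject who lacks that score. The comparison of those who remain is safe if missingness is unrelated to outcome. It is also safe if missingness is related to outcome but both the dropout rate and its relation to outcome are the same in each arm. The plan itself expects unequal rates, and some subjects left because of hip arthroplasty, so a link with outcome is plausible.

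Enrolling more subjects narrows the confidence interval around whatever the completer difference estimates; it does not move that difference towards the randomised one. Meanwhile, baseline and earlier mHHS from non-responders, which carry information about their missing scores, play no part in the between-arm test. At stake is a 24-month difference that partly reflects who answered.

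**Working it through.** **1. The missing share.** 47 − 31 = 16 = 5 + 11. Yield is 31/47 = 65.96% (the plan prints 65.95%, truncated), so 16/47 = 34.0% are missing. The Wilson 95% interval for the yield is 52 to 78%. If all 11 outstanding surveys later arrived, the missing share would be 5/47 = 10.6%. No 12-month figure is given.

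**2. The enrolment response.** 70/0.6596 = 106.1, so 107 subjects would be expected to give 70 completers; 122 × 0.6596 ≈ 80. The mismatch with 122 is a separate matter. What counts here is that sample size does not enter the bias formula in step 4.

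**3. The SD.** None is stated. From 35 per arm, a 10-point difference, one-sided 5% and 80% power:
SD = 10 / [(1.645 + 0.842) × √(2/35)] = 10 / 0.594 = 16.8, or 16.7 with the t distribution.

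**4. The bias by arithmetic.** Let m be the missing share in an arm and g the mean of missing minus observed scores. The completer mean exceeds the full mean by −m × g. Hence
bias (surgery − PT) = −m_S g_S + m_C g_C.
The split by arm and the gaps below are assumptions; a positive bias favours surgery.

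| Missing, surgery / PT | Gap, surgery / PT | Bias (points) |
|---|---|---|
| 34% / 34% | −10 / −10 | 3.4 − 3.4 = 0 |
| 40% / 28% | −5 / −5 | 2.0 − 1.4 = 0.6 |
| 40% / 28% | −10 / −10 | 4.0 − 2.8 = 1.2 |
| 40% / 28% | −15 / −15 | 6.0 − 4.2 = 1.8 |
| 34% / 34% | −10 / 0 | 3.4 |
| 40% / 28% | −10 / 0 | 4.0 |

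Unequal dropout alone gives no bias (set both gaps to 0). An equal gap with equal rates gives none either.

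**5. Simulated trials.** Assumed: 61 per arm, SD about 16.7, 12-to-24-month correlation about 0.7 (range 0.6 to 0.75), no true difference, and 24-month response depending on the 12-month score.
- Same slope in both arms (odds ratio 1.6 to 2.7 per SD), yields 57.4% surgery and 74.5% PT (a gap of 17.1 percentage points): bias 0.8 to 1.6 points.
- Same-slope case with an 8-percentage-point gap in yields: 0.4 to 0.75. With a 3-percentage-point gap: 0.2 to 0.3.
- Slope in surgery only (odds ratio 2.2): about 3 to 3.5 points, two-sided type I error 12 to 15%. With equal 66% yields it is 2.3 to 3.0 points and 9 to 14%.
- Response unrelated to score: no bias.

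**6. What using all scores recovers.** If every non-responder has a 12-month score and response depends only on that score, an all-data likelihood estimate is within about 0.1 point of the truth. In the surgery-only case, about 0.9 to 1.0 of 3.5 points remains if half of the non-responders also lack a 12-month score, and 2.7 remains if all do. If response depends on the 24-month score itself, 2.7 of 5.0 points remains.

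**The case against.** Several points on the other side stand.
- The plan nowhere adopts a completer analysis set. The sentence about 70 completers is about sample size; the completer effect is inferred from the test together with the silence on missing scores.
- A reader might infer that a third of the data is missing from the 12-month test. The documents do not support that: the 34% is a 24-month snapshot, and some of the 11 outstanding surveys may have arrived later.
- A reader might infer that higher enrolment was the only response to poor yield. Section III lists real retention measures.
- A reader might infer a bias that is large against the 10-point target. The documents give no dropout split by arm, no gap between missing and observed scores, and no sign that low scorers leave in surgery only. The larger figures rest on that last assumption.
- The good performance of the all-data estimate is partly built in, because the main scenarios are missing at random given an observed 12-month score.
- The issue is not cleanly separate from hip arthroplasty, since some of the 5 exits were for that reason.

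These limits narrow the point to the 24-month comparison and lower confidence in its size. They do not supply a missing-data method, and retention measures cannot stand in for one: the 11 surveys were outstanding after multiple contact attempts.

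**Conclusion.** The point holds in this form: the 24-month part of the primary outcome is to be tested, as far as the plan says, on responders only, with about a third of scores missing at the last count, unequal dropout expected, and no method or sensitivity analysis to deal with it. Bias is possible, not demonstrated.

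Its plausible size runs from about 0.2 to 1.6 points when the dropout slope is the same in both arms, depending on the assumed gap in yields. It reaches about 3 to 3.5 points, roughly a third of the target difference, only if low scorers drop out in surgery alone. All of this rests on an SD back-solved from 35 per arm and on assumed correlations, yields and slopes. The type I error figures are two-sided, whereas the sample size uses a one-sided test.

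Nothing here shows that the 12-month comparison is biased. Nor can a model be promised to remove the bias entirely: it removes the part that observed scores explain. The change should be made because it is cheap and uses scores the trial already collects.

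**What to change.** - Replace the separate between-arm t-tests with one likelihood-based repeated-measures model on all randomised subjects: arm by time, unstructured covariance, with baseline, 12-month, 24-month and any interim mHHS that falls in a defined visit window. Report the 12- and 24-month contrasts. Multiple imputation with baseline adjustment would be an acceptable equivalent.
- Define the visit windows first, because surveys are tied to ordinary clinic visits and no mHHS schedule is listed.
- State separately how scores after hip arthroplasty and after crossover enter. Left as missing, scores after arthroplasty would be predicted as if no replacement had occurred.
- Add a delta-adjusted (tipping-point) sensitivity analysis that lowers missing scores by arm, and report the shift at which the conclusion changes.
- Report missing scores by arm, reason and time point, including 12 months.
- Keep the 70 completers as a planning figure only, and correct the repeated reference to 12 months if 24 was meant.

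The cost is analysis-plan wording and modest programming, with no new data, visits or enrolment. The downside is reliance on missing at random in the main analysis, which the tipping-point analysis is there to probe. Any gain in precision depends on the scenario (from about 3% higher to 19% lower variance than the t-test) and is not the reason for the change.

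### The stated yield of 31/47 gives 107–108 subjects for 70 completers, not 122, and the 80% power ignores the permitted PT-to-surgery crossover and leaves the analysis set undefined

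*Combined protocol and SAP*

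**What the plan says.** In Section V, Power Analysis, Specific Aim 1, the plan takes a 10-point mHHS difference and "a single-tail independent t-test to evaluate the difference between means with 80% power and a 5% significance level, 35 subjects are needed". Two 35-subject arms give the 70-completer target. The SD is not printed.

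On attrition, the same section first reports that "we expected a 7.3-10.3% dropout rate based on the results of a similar study in the knee". It then turns to the trial's own experience to July 2018. Of 47 patients past two years, 5 had left and 11 had not returned their 2-year surveys. It concludes: "With a yield of 31 patients out of 47, or 65.95%, we increased our sample size to 122". The target follows: "we estimate needing 122 subjects to achieve 70 study completers, in the appropriate proportion of 35 subjects per treatment arm". Two further statements bear on the number: "We enroll until reaching at least 35 subjects in each group", and, from the knee trial, "we can expect a higher drop-out rate in the surgical group". No drop-out figure by arm is given.

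On crossover, Section IV (Physical Therapy Visits) makes failure of the advancement criteria a trigger for referral back to the surgeon. It also lets subjects choose surgery, not before 6 weeks after enrolment. Section VIII, item 1.a, repeats that the PT arm may cross over. Aim 4 in Section II is devoted to subjects who do.

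Section V, Hypothesis 1.1-1.4, compares mean mHHS between groups at 12 months with independent t-tests and says nothing about crossovers. Section III makes 12 and 24 months both primary.

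**The concern.** The sample-size sentence reads as a derivation, so a reader should be able to get from 70 completers and the observed yield to 122. If not, nobody can tell whether 122 is meant to secure 70 completers, about 80, or a margin for filling the weaker arm.

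The crossover gap matters more. Crossover is part of the design and can happen well before either primary time point. If crossovers stay in the PT arm, the expected difference shrinks and the 80% describes a trial that will not be run. If they are moved or dropped, the arms are no longer compared as randomised, because poor response to PT is itself a route to crossover. A diluted null result could be misread as showing that PT does as well as surgery, and the background section says the trial might support recommending conservative care. Leaving the analysis set open also leaves the choice to be made after the data are seen.

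**Working it through.** **Sample size.** All inputs are from Section V, Power Analysis, Specific Aim 1.

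- Yield: (47 − 5 − 11)/47 = 31/47 = 0.6596. This reproduces the plan's percentage apart from rounding.
- Subjects for 70 completers: 70/0.6596 = 106.1, so 107. By arm: 35/0.6596 = 53.06, so 54 per arm, or 108.
- Completers from 122: 122 × 0.6596 = 80.5, about 40 per arm.
- Excess over the stated inputs: 122 − 108 = 14, or 122 − 107 = 15.

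Two unstated routes reach 122:

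- The earlier drop-out range applied as well. At 10.3%: 35/0.897 = 39.02, so 40 per arm; 80/0.6596 = 121.3, so 122. At 7.3% the same steps give 38 per arm and 116. This would count departures twice, because 31/47 already excludes the 5 who left (5/47 = 10.6%).
- A lower surgical yield. 35/61 = 57.4% in the surgical arm would require 61 per arm. No yield by arm is given.

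The margin has value. Assume a 31/47 yield in each arm, independent binomial counts, and no enrolment beyond the stated number. Both arms then reach 35 with probability 0.88 at 61 + 61, against 0.40 at 54 + 54.

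**Power under crossover (illustration).** The SD, the crossover rate c, the fraction b of surgical benefit that crossovers obtain, and the 12-month yield are assumptions. The documents give none of them.

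- SD: solving for 80% power with 35 per arm, one-sided 5%, 10 points gives 10 × √(35/2)/(1.645 + 0.842) = 16.8 by the normal approximation, and 16.7 with the t distribution. Because it is back-solved, it does not verify the 80%.
- As-randomised difference: δ = 10 × (1 − c × b).
- Power: noncentral t with 2n − 2 degrees of freedom, noncentrality δ/(SD × √(2/n)), one-sided 5%.
- Completers per arm: 61 × 31/47 = 40.2, so 40, at the 2-year yield. If the 11 subjects without 2-year surveys had 12-month data, the yield would be 42/47 and 61 × 42/47 = 54.5, so 54.

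| SD 16.7 | c = 0 | 10% | 20% | 30% |
|---|---|---|---|---|
| 40 per arm (2-year yield), full benefit | 85% | 77% | 69% | 59% |
| 40 per arm, half benefit | 85% | 81% | 77% | 73% |
| 54 per arm (assumed 12-month yield), full benefit | 93% | 87% | 80% | 70% |

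With full benefit, the crossover rate at which power drops below 80% is:

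| | SD 15 | SD 16.7 | SD 18 |
|---|---|---|---|
| 40 per arm | about 16% | about 7% | below 80% with none |
| 54 per arm | about 28% | about 20% | about 13% |

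Treating crossovers as average PT subjects is a simplification, since poor responders are more likely to cross.

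**The case against.** **The number errs on the safe side.** This stands. The mismatch does not lower power, and a reader who infers that 14 or 15 subjects could be cut would be wrong. The plan expects worse surgical retention and needs 35 in both arms, which 108 would often miss even at equal yields.

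**The plan may have had a sound reason for 122.** It may. One might infer that the authors counted drop-out twice, but that route is a reconstruction, and a margin for surgical drop-out fits equally well. The text supports neither over the other. What can be said is that the printed inputs do not give the printed result.

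**Crossovers are already kept distinct.** Aim 4 compares them with subjects initially randomised to surgery, which makes counting by treatment received less likely. It does not settle how they enter the Hypothesis 1.3 comparison.

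**The power loss rests on assumptions, and the yield is a 2-year figure.** Both are right. The retention section in Section III expects roughly 90%, close to 42/47 = 89.4%, and at such a 12-month yield much more crossover is tolerable. With half benefit and SD 15, power with 40 per arm stays at 81% even at 30% crossover. The documents therefore do not support a flat claim that modest crossover takes power below 80%, or that the trial is underpowered.

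**Analysis by randomised arm meets another obstacle.** Section III removes surgical subjects found to have unexpected pathology at arthroscopy. This exclusion comes after randomisation and can arise only in those who have surgery, so any fix has to deal with it.

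**Conclusion.** The point holds in two parts of unequal weight.

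The lesser part is arithmetic and certain: 70 completers at 31/47 require 107 subjects (108 with equal arms), and 122 corresponds to about 80 completers. The error is upward and harmless to power. It needs an explanation, not a smaller trial.

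The greater part is an omission, also certain: the 80% contains no crossover allowance, and the analysis set for the main between-arm test is not named. Its size is uncertain. At SD 16.7 and full benefit in crossovers, 20% crossover means about 69% power with 40 per arm and about 80% with 54 per arm. Half benefit at 40 per arm gives 77%. These figures depend on the assumed SD, crossover rate, benefit and yield, and on analysis as randomised with a one-sided 5% test. They show that a single 80% is not informative; they do not show that power is inadequate. This should be fixed before analysis.

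**What to change.** - Keep 122. Either restate it as giving about 80 completers (40 per arm) at the observed 2-year yield, or state the margin it contains for reaching 35 in both arms when surgical drop-out is higher.
- In Section V, Hypothesis 1.1-1.4, specify that the primary between-arm comparison is by randomised arm with crossovers kept in the PT arm, and that the 35-per-group target counts completers by randomised arm.
- Reconcile this with the Section III rule that removes surgical subjects with unexpected pathology, and say how those subjects enter the comparison.
- State the SD behind 35 per arm.
- Replace the single 80% with a small table of power over a stated range of SD and crossover, labelled 12 or 24 months, with the assumed yield for each.

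The cost is a reworded power section, a sentence or two on the analysis set, and one table. The downside is that the stated power may fall below 80% in some scenarios. Neither enrolment nor the crossover rules change.

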We plan to track the effects of OA on outcomes through identification and localization of OA at the time of arthroscopy using a mapping technique (see diagram). After complete visualization of the intra-articular space, as is standard practice in hip arthroscopy, classification of any existing osteoarthritis will be done according to the Outerbridge grading scale. Using this system, we are able to categorically group subjects based on location and severity of disease. If multiple lesions are present, subjects will be characterized by the most severe grade. Furthermore, based on the data gathered through meeting hypotheses 1.1-1.4, we will subdivide primary outcome scores into four categories.⁶⁰ Category I, excellent outcomes (mHHS ≥ 90); Category II, good outcomes (mHHS ≥ 80); Category III, fair outcomes (mHHS ≥ 70), and Category IV, poor outcomes (mHHS < 70). The likelihood of outcomes based on Outerbridge grading and outcome category will be determined through odds ratios. Analysis will be carried out using Chi-squared tests. Significance is set at $P < 0.05$. Linear regression analysis will be performed to detect if any relationship exists between the severity of osteoarthritis and short-term outcome scoring.

Hypothesis 3.1:

This is an exploratory hypothesis whose assessment will no influence the other data sets. Prior work by other groups has demonstrated that evaluation of arthritic burden by conventional measures (Kellgren-Lawrence and Tonnis grading) are not indicative of the severity of arthritis found at the time of arthroscopy.⁵⁸ We will explore this phenomenon in our own cohort of subjects, specifically those in the surgical group and report our findings. We will correlate our findings for significance.

Power Analysis:

Specific Aim 1, Hypotheses 1.1-1.4: *To evaluate if physical therapy alone or arthroscopic labral repair and physical therapy is of greater benefit to patients presenting at age 40 with tears of the acetabular labrum.*

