Hypothesis 2.1 was powered on the basis of our prior work where 33% of study participants had grade 4 Outerbridge changes the time of arthroscopy. Dividing our cohort into two subgroups: 1) Those with grade 4 changes and 2) Those without. We will need 12 subjects with grade 4 changes in order to perform adequate sub-group analysis.⁶³ Powered to 80% and 5% significance level. Hypothesis 2.2 is another sub-group analysis that will be conducted in a similar fashion to that of hypothesis 2.1. However, the two groups will be categorized into: 1) cartilage defects at or near the chondro-labral junction and 2) cartilage defects not at or near the chondro-labral junction. We cannot control the heterogeneity of the subjects enrolled, but based on this analysis we expect to meet our target enrollment. Hypothesis 2.3 will be analyzed via linear regression and is appropriately powered.

Specific Aim 3 is exploratory. Since we are recruiting subjects for the main purposes of determining outcomes, we recognize that we may be underpowered for the definitive analyses of our radiographic correlation hypotheses. Nevertheless, we anticipate that we will enroll sufficient numbers of subjects to draw an association or at the very least, trend patient outcomes with degree of joint space narrowing, Kellgren-Lawrence grading, and Tonnis grading. There should also be sufficient numbers to preliminarily assess any correlations between pre-operative Kellgren-Lawrence and Tonnis grades with the Outerbridge classification at the time of arthroscopy.

VI. RISKS & DISCOMFORTS

Conservative Treatment: Subjects can expect the routine discomfort associated with any therapeutic procedure. Complications may include muscle soreness, pain, and increased edema or muscle fatigue.

Operative treatment: Since surgery is not considered a research procedure (only the randomization into the surgery group is considered a research procedure, as explained above) surgical risks are explained in the surgical consent process.

In the rehabilitation period, patients will be subject to the same potentials discomforts as those subjects in the conservative treatment group as the physical therapy protocols for both groups are identical. In both treatment groups every effort will be made to minimize the risk of adverse events and patient discomfort.

VII. POTENTIAL BENEFITS:

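### The 80% power stated for Hypothesis 2.1 rests on a prevalence alone and cannot be verified; at Aim 1's own standardised effect, 12 v 23 subjects give about 37% (two-sided) or 50% (one-sided)

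*Combined protocol and SAP*

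**What the plan says.** Hypothesis 2.1 (section II, Specific Aim 2) concerns the surgical group only. It predicts worse results, chiefly on the mHHS, with grade 4 change than with grade 3 or less.

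The power section for Specific Aim 2 (section V) states: "Hypothesis 2.1 was powered on the basis of our prior work where 33% of study participants had grade 4 Outerbridge changes". It continues "We will need 12 subjects with grade 4 changes in order to perform adequate sub-group analysis" and ends "Powered to 80% and 5% significance level".

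The analysis section for Hypotheses 2.1 to 2.3 splits the mHHS into four outcome categories and plans odds ratios. It adds "Analysis will be carried out using Chi-squared tests" and a linear regression of short-term score on arthritis severity. The 80% is tied to none of these.

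The power section for Specific Aim 1 supplies the group sizes. It takes "a 10 point or greater difference on the mHHS as significant, and a single-tail independent t-test", with 80% power at the 5% level, and arrives at 35 per arm. It also says "We enroll until reaching at least 35 subjects in each group" and "With a yield of 31 patients out of 47, or 65.95%, we increased our sample size to 122". It expects more drop-out after surgery: "As such, this cohort may be our limiting factor".

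The Preliminary Data in section I give an odds ratio of 2.5 for arthroscopically identified arthritis and 7 for age as predictors of poorer outcome.

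**The concern.** A power figure needs a target effect, a measure of spread (or event rates), a test with its sidedness, and both group sizes. For Hypothesis 2.1 the plan gives a prevalence and one group size. The 12 therefore looks like an expected head count to which a power statement was attached.

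What is at stake is how a null result would be read. With 80% power on record, a reader may take a null as evidence that grade 4 change does not matter after repair. If the true effect is near 10 mHHS points or an odds ratio of 2.5, a null is much more likely than the stated 20%. The Implications part of section I wants age and arthritic burden used to identify who benefits from repair, so the reading matters.

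A separate, smaller point is that grade 4 versus lower is not a randomised contrast, and no covariate is named. The plan's background calls age the stronger predictor and says older patients with symptomatic tears are more likely to have osteoarthritis. An unadjusted comparison can show that grade 4 subjects do worse, but cannot separate arthritis from age.

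**Working it through.** **1. Where the 12 comes from.** Inputs: prevalence 33% (power section, Aim 2) and 35 surgical completers (power section, Aim 1). 0.33 x 35 = 11.55, rounded up to 12, leaving 35 - 12 = 23 for comparison. The stated 80% cannot be reproduced, because no effect, SD or sidedness is given.

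**2. Effect implied by Aim 1.** Inputs: 35 per arm, one-sided 5%, 80% power, 10 points.
- Normal approximation: d = (1.645 + 0.842) x sqrt(2/35) = 0.594.
- Noncentral t: d = 0.600, so SD = 10/0.600 = 16.7.

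The plan states no SD, so 16.7 is an assumption obtained by inverting its own sample size.

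**3. Group sizes examined.**
- 35 surgical completers: 12 v 23.
- The plan's two-year yield, assuming a 1:1 split: 122 x 31/47 = 80.5, or about 40 per arm; 0.33 x 40 = 13.2, so 13 v 27. Short-term data may be more complete than this yield.
- No loss at all: 61 in the surgical arm; 0.33 x 61 = 20.1, so 20 v 41.

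**4. Power for 10 points and the effect needed for 80%.** Noncentral t with noncentrality d / sqrt(1/n1 + 1/n2) and n1 + n2 - 2 degrees of freedom. For 12 v 23 the noncentrality is 0.600/0.356 = 1.69. Entries are two-sided / one-sided.

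| Grade 4 v lower | Power at d = 0.600 | d needed for 80% | Points at SD 16.7 |
|---|---|---|---|
| 12 v 23 | 37% / 50% | 1.03 / 0.90 | 17.1 / 15.1 |
| 13 v 27 | 41% / 54% | 0.97 / 0.86 | 16.2 / 14.2 |
| 20 v 41 | 58% / 70% | 0.78 / 0.69 | 12.9 / 11.4 |

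The third column needs no SD. Against Aim 1, 1.028/0.600 = 1.71 and 0.904/0.600 = 1.51.

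**5. Sensitivity to the SD.** Power for 10 points at 12 v 23, two-sided / one-sided: SD 12, 62% / 74%; SD 14, 50% / 63%; SD 20, 28% / 39%. One-sided 80% needs an SD of at most 11.06. At that SD, Aim 1's one-sided test would need 16 per arm, not 35.

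**6. The odds ratio of 2.5.** The plan does not define its event or comparator rate. I collapsed the outcome to two categories and assumed comparator rates of 10% to 70%. Exact power of the Pearson chi-squared test, two-sided / one-sided:
- 12 v 23: 13-26% / 26-36%
- 13 v 27: 15-27% / 27-41%
- 20 v 41: 24-38% / 35-51%

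**7. Chance of obtaining 12 grade 4 subjects.** Binomial with p = 0.33, P(X >= 12): 50% with 35 surgical completers, 71% with 40, 99% with 61.

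**The case against.** The strongest reply is that nothing stated is shown to be wrong. The 80% may rest on assumptions in the earlier series that were simply not written down, and that 12 was derived as 0.33 x 35 is an inference. Ten points is Aim 1's difference between surgery and physical therapy, not a target for grade 4 versus lower. The SD of 16.7 is back-solved, and the spread within the surgical arm may differ. This stands, and it is why the point is that the claim cannot be verified. The 37% and 50% are benchmarks, not the true power.

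A smaller SD does help: at SD 14 with no loss (20 v 41), one-sided power for 10 points is 83%. But at SD 14, Aim 1 would need about 2 x (1.645 + 0.842)^2 x (14/10)^2 = 24.2, or 25 per arm, which does not fit its 35. Other readings of Aim 1 do not restore 80% at 12 v 23. Taking its test as two-sided (d = 0.68) gives 46% / 59%; taking 35 as the total (d = 0.86) gives 65% / 76%.

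The plan does not say whether subjects who cross over to surgery enter Hypothesis 2.1. Counting all 70 completers (0.33 x 70 = 23.1, so 23 v 47) gives 64% / 75% at d = 0.600. The 50% chance of reaching 12 is a low case, since 35 is a minimum.

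The odds-ratio exercise rests on assumed rates, and regression on the full grade scale was not evaluated. Hypothesis 2.1 also makes no causal claim, so adjustment is a separate improvement rather than part of the power discrepancy.

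**Conclusion.** The concern holds. The 80% for Hypothesis 2.1 has no stated effect size, SD, sidedness or comparison-group size, and the 12 is consistent with an expected count rather than a power calculation. The firmest result is free of any SD: 12 v 23 delivers 80% only for a standardised effect of about 0.9 to 1.0, some 1.5 to 1.7 times the one on which Aim 1 was sized. With Aim 1's implied SD, neither effect that could be borrowed from the documents (10 points or an odds ratio of 2.5) reaches 80% at any of the three group sizes, even with no loss.

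This does not show that every plausible effect is underpowered. It depends on Aim 1 being read as written, and the odds-ratio figures depend on assumed event rates. Aim 1 itself is unaffected. The age point is secondary: the contrast behind the odds ratio of 7 is undefined and enrolment starts at 40, so its size may not carry over. The correction should be made, but it concerns a secondary aim.

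**What to change.** Withdraw the 80% for Hypothesis 2.1, or replace it with the mHHS difference detectable with 80% power at the expected group sizes, using the SD from the sponsor's retrospective data and a named test and sidedness. If the sponsor holds the missing assumptions, stating them settles the power point. Otherwise label the hypothesis exploratory and report 95% confidence intervals.

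In the linear regression already planned, fit grade 4 versus 3 or less adjusted for age and baseline mHHS, and report it beside the unadjusted odds ratios and chi-squared tests.

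The cost is SAP wording; both covariates are already collected. The price is a less favourable power statement, two degrees of freedom, and a somewhat wider interval if age and grade are correlated. Adjustment should not be presented as a rescue. Assume SD 16.7, a multiple correlation R of covariates with outcome of 0.3 to 0.5, and a correlation r of covariates with grade of 0 to 0.3, none of which is in the documents. Multiplying d by sqrt(1 - r^2)/sqrt(1 - R^2) gives 37-47% two-sided or 50-60% one-sided at 12 v 23, and 41-52% or 54-64% at 13 v 27. Only the best case at 20 v 41 (no loss, one-sided, R = 0.5, r = 0) reaches 81%.
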